### ***3.1.4 Definition of Dose Limiting Toxicity (DLT)***

An acute DLT will be defined as RTOG grade 3 or greater, acute GI or GU toxicity (see appendix IIA) within 3 months after the completion of radiation. Thus, accrual to an escalated dose cohort may need to be delayed so that all 3 patients in the current cohort are followed for 2 months. Given that the volume of normal tissue irradiated to standard dose or higher will be substantially limited, late toxicity is less of a concern than acute toxicity.

### ***3.1.5 Definition of Maximum Tolerated Dose (MTD)***

The primary objective is to estimate the MTD of external beam radiation that results in limiting acute toxicity. The MTD is defined as the dose level immediately below the dose level at which 2 or more in a cohort of either 3 or 6 patients experienced a DLT attributed to radiation therapy. If DLT does not occur at the highest dose level the protocol will be amended to escalate by 10% in cohorts of 3 patients each with the standard 3-6 dose escalation procedure.

## **3.2 PROTOCOL ADMINISTRATION**

### ***3.2.1 MR Imaging Guidelines***

In all patients, conventional anatomic imaging (Fast spin echo T2 weighted scans) in the axial and coronal oblique planes will be obtained for research purposes to define the extent of the tumor. An endorectal coil may be indicated for prostate exams.

Following conventional anatomic imaging, one or more of the following research biological imaging tests will be performed. Examples include but are not exclusive to:

**a) MR Spectroscopic Imaging (MRSI)**

Using standard FDA approved spectroscopy software (General Electric Medical Systems, Milwaukee, WI), this will be performed using multiple voxels at multiple slices (“multivoxel-multislice MR spectroscopy”) which will generate a spectroscopic map of the area of interest reflecting the relative concentrations of various metabolites in the hydrogen resonance spectrum including citrate, choline, creatine, choline and lipids. This procedure may require approximately 30-45 minutes of scanning.

**b) Dynamic Contrast Enhanced MRI**

This imaging study uses 1mmol/kg of an FDA approved Gadolinium chelate administered slowly by intravenous injection. Serial 3D dynamic enhanced MRI may be performed through the area of interest over a period of approximately 10 minutes. These data will be sent electronically to an independent workstation where a pixel by pixel time-signal intensity curve will be generated. This data will be automatically fit to a two compartment pharmacokinetic model using a custom designed image processing algorithm which will be used to generate semiquantitative parameters reflecting flow ("A") and vessel permeability ( $k_{ep}$ ). These parameters will be used to create color encoded maps which reflect the vascular flow and permeability of various regions.

c) BOLD

To accomplish this, the patient will first breathe room air via a regulated and non-magnetic tank set at 10L/min for 5 minutes via a specially designed breathing apparatus designed by [name]. of the Anesthesia Department. This breathing apparatus consists of a mouth piece and a clamp is place on the nose. It is non-invasive, and the patient can let go of the mouth piece if they find it uncomfortable.

Following this baseline study, the inhaled gas will be switched to regulated medical grade carbogen (5% carbon dioxide and 95% oxygen) in non-magnetic tanks administered at 10-15L/min for 7 minutes. This will improve the oxygenation of tissue by a combination of hyperoxia due to the high oxygen content and vasodilation due to carbon dioxide. Following carbogen inhalation the patient will be switched back to the room air at prior rates for 5 minutes. Images will be analyzed by measuring the difference in signal between the room air and carbogen scans and color maps reflecting per cent change in signal intensity will be generated for comparison.

d) OTHER Sequences

Other MRI sequences may be obtained. However, these other sequences will involve novel pulse sequences or post-processing of image data that will be transparent to the patient and will not require any additional procedures to be performed.

Of note, given the time required to perform and analyze these sequences as well as the length of the biopsy procedure, patients may have the target imaging with various high resolution sequences done at a separate time from the biopsy itself.

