#### *1.2.5 The 'APT-MRI' system*

In collaboration with Department of Biomedical Engineering at Johns Hopkins we have developed a system that provides transrectal needle access to the prostate while a patient is imaged inside of a 'closed' scanner. This system, called the APT-MRI system (Access to Prostate Tissue under MRI-guidance), will be utilized in this study to acquire needle biopsy tissue in accurate reference to DCE-MRI images.

[figure not shown]
The method is very similar to transrectal ultrasound guided biopsy of the prostate, except that it is applicable within a closed high-field MRI scanner. In canine studies, accurate needle placement in a variety of clinical applications (e.g. biopsy, injections, and seed placement) were demonstrated.[19] This system was adapted to clinical use and investigated for feasibility, tolerability, and needle targeting accuracy under protocols 03-C-0190 and 02-C-0167.

Clinical results to date show that the APT-MRI system is safe, well tolerated, and can target prostatic sites with millimeter accuracy.[20] We used the 'APT-MRI' system to place gold fiducial markers within the prostate gland in patients with localized prostate cancer in order to assess not only needle placement accuracy, but also the accuracy with which the tissue itself was targeted (i.e. leaving a permanent marker allows for measurement of the impact of tissue deformation, produced during needle insertion, on targeting accuracy). Subsequently, the system was also used for four 1.5T MRI-guided prostate biopsy procedures in three patients.

[figure not shown]
The mean MR procedure duration was 72 minutes and was well tolerated. Using axial MR images, needle and marker placement errors were assessed (see figures 1& 2). The mean needle placement accuracy was 1.9 mm for the fiducial marker placement studies and 1.8 mm for the biopsy procedures. The mean fiducial marker placement accuracy was 4.8 mm and the mean transverse fiducial marker placement accuracy was 2.6 mm. The gold fiducial markers were subsequently used to assess daily setup errors and off-line organ motion during a standard course of external beam radiation therapy for prostate cancer.

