#### 2.1.2 *Exclusion Criteria*

- 2.1.2.1 Cognitively impaired patients who cannot give informed consent.
- 2.1.2.2 Patients with metastatic disease.
- 2.1.2.3 Contraindication to biopsy
  - Bleeding disorder
  - PT/PTT  $\geq$  1.5 times the upper limit of normal
  - Platelets  $\leq$  50K
  - Artificial heart valve
- 2.1.2.4 Contraindication to MRI
  - Patients weighing  $>136$  kgs (weight limit for the scanner tables)
  - Allergy to MR contrast agent
  - Patients with pacemakers, cerebral aneurysm clips, shrapnel injury or implantable electronic devices.
- 2.1.2.5 Pre-existing and active prostatitis or proctitis.

2.1.2.6 Other medical conditions deemed by the PI or associates to make the patient ineligible for protocol investigations, procedures, and high-dose external beam radiotherapy.

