### 8.3 MRI CONTRAST AGENT – Gadopentate dimeglumine

Manufacturer: Berlex Laboratories, Wayne NJ

Commercial name: Magnevist

Description: This is an FDA approved contrast agent in widespread use. Gadolinium produces MR contrast by altering the relaxivity of neighboring water protons. Experience at NIH has been obtained with over 30,000 intravenous injections.

Form: Gadopentate dimeglumine is available as Gd-DTPA. It is available as a sterile injectable liquid in single use ampules of 20 ml. The inactive ingredients are meglumine and diethylenetriamine pentaacetic acid.

Supply: Magnevist is commercially available and will be supplied by the Clinical Center Department of Radiology

Toxicities: The serious reaction rate (asthma, hives, seizures, hypotension) is less than 0.5%. The dose is 0.1 mmol/kg BW administered IV bolus via mechanical injector. There are no contraindications for its use. Gd-DTPA can be used in patients with elevated Cr. Levels and does not have known nephrotoxicity. Possible complications relate to extravasation of contrast in which localized swelling and pain may develop but because of the small volume (20cc) this does not lead to skin necrosis. There may be headache, nausea, vomiting, and transient sensations of heat or cold or taste disturbances following injection of gadopentetate.

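### Section 3.2.1 b) gives gadolinium at 1 mmol/kg, ten times the 0.1 mmol/kg in section 8.3, and the two sections also disagree on how it is injected

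*Combined protocol and SAP*

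**What the plan says.** Two sections of the protocol give a contrast dose.

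- Section 3.2.1 b), Dynamic Contrast Enhanced MRI, falls under Protocol Administration: "This imaging study uses 1mmol/kg of an FDA approved Gadolinium chelate administered slowly by intravenous injection". It does not name a product.
- Section 8.3 is headed "MRI CONTRAST AGENT – Gadopentate dimeglumine" and is the only MR contrast agent listed in section 8. It says: "The dose is 0.1 mmol/kg BW administered IV bolus via mechanical injector". On supply: "It is available as a sterile injectable liquid in single use ampules of 20 ml". On extravasation, it reasons that "because of the small volume (20cc) this does not lead to skin necrosis".

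On how many patients are concerned, section 3.2.1 says that "one or more of the following research biological imaging tests will be performed", and dynamic contrast MRI is one of those listed. Section 1.2.5 suggests wider use: the biopsy system "will be utilized in this study to acquire needle biopsy tissue in accurate reference to DCE-MRI images".

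**The concern.** The two sections instruct staff differently about the same procedure. The dose differs tenfold, one section calls for slow injection and the other for a bolus, and the protocol does not say which section governs. Section 3.2.1 is the operative imaging section, so it cannot be set aside as background.

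Anyone who followed 3.2.1 b) literally would give ten times the dose that 8.3 supports. The reassurances in 8.3 (serious reactions below 0.5%, no skin necrosis on extravasation, use permitted with raised creatinine) all stand beside 0.1 mmol/kg and a volume of about 20 cc. Nothing in the protocol offers safety support for 1 mmol/kg.

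There is also a smaller measurement issue. Section 3.2.1 b) fits the enhancement data to a two-compartment pharmacokinetic model, and an unsettled dose and mode of injection leave that imaging method undefined.

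**Working it through.** **Inputs**

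| Quantity | Value | Source |
|---|---|---|
| Dose and mode, imaging section | 1 mmol/kg, slow IV | 3.2.1 b) |
| Dose and mode, drug section | 0.1 mmol/kg, IV bolus by mechanical injector | 8.3 |
| Volume in the extravasation statement | 20 cc | 8.3, Toxicities |
| Ampule size | 20 ml | 8.3, Form |
| Upper body weight ("weight limit for the scanner tables") | 136 kg | 2.1.2.4 |
| Concentration | not stated; 0.25, 0.5 and 1.0 mmol/mL assumed | assumption |
| Other body weights | 60 and 80 kg | assumption |

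The plan contains no derived figure to reproduce. The closest is the pairing of 0.1 mmol/kg with 20 cc in 8.3, which step 3 tests.

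**Step 1. Ratio and absolute dose.** The ratio is 1 / 0.1 = 10, whatever the weight or concentration. Dose in mmol = mmol/kg × kg:

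- 80 kg: 0.1 × 80 = 8 mmol against 1 × 80 = 80 mmol.
- 136 kg: 0.1 × 136 = 13.6 mmol against 1 × 136 = 136 mmol.

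**Step 2. Volume, without assuming a concentration.** If 20 cc holds the 8.3 dose, the same agent at 1 mmol/kg needs 20 × 10 = 200 cc, and 200 / 20 = 10 ampules.

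**Step 3. Volume over assumed concentrations.** Volume (mL) = dose (mmol/kg) × weight (kg) / concentration (mmol/mL). At 80 kg:

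| Concentration (mmol/mL) | Volume at 0.1 mmol/kg | Volume at 1 mmol/kg | Ampules at 1 mmol/kg |
|---|---|---|---|
| 0.25 | 32 mL | 320 mL | 16 |
| 0.5 | 16 mL | 160 mL | 8 |
| 1.0 | 8 mL | 80 mL | 4 |

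At 0.1 mmol/kg the volumes are of the same order as 20 cc. At 1 mmol/kg even the smallest is four times 20 cc.

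**Step 4. Body weight that 20 mL would serve.** Weight (kg) = 20 × concentration / dose:

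- At 0.1 mmol/kg: 50, 100 and 200 kg for 0.25, 0.5 and 1.0 mmol/mL.
- At 1 mmol/kg: 5, 10 and 20 kg.

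Section 2.1.1.6 admits only adults, so within the assumed range 20 cc cannot be a 1 mmol/kg dose in this trial.

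**Step 5. Concentration needed for 20 mL to hold the dose.** From 60 to 136 kg this is 0.1 × 60 / 20 = 0.30 to 0.1 × 136 / 20 = 0.68 mmol/mL at 0.1 mmol/kg. At 1 mmol/kg it is 60 / 20 = 3.0 to 136 / 20 = 6.8 mmol/mL. The two ranges do not overlap, so one agent cannot fit both doses to about 20 mL.

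**Step 6. Effect of the correction.** With 0.1 mmol/kg in 3.2.1 b), the doses agree. The slow-versus-bolus conflict would remain and needs its own correction.

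**The case against.** The strongest objection is that the tenfold claim rests on one missing character in text read from a PDF by a program. If a decimal point was lost in reading, the dose conflict disappears and only the injection wording is left. That possibility cannot be excluded. However, no garbling is visible around the figure, and the document writes leading zeros elsewhere. The slow-versus-bolus difference is separate evidence that the sections were not aligned, but it does not settle whether a decimal was dropped.

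Second, 8.3 is the specific drug entry, with product, dose, device and supplier, and staff might well follow it. Drawing up about ten single-use ampules would also prompt a question. Both points make actual overdosing less likely. They do not remove the conflict, because nothing says that 8.3 prevails and the protocol describes no check on the contrast dose.

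Third, the volume argument is not exact. At 0.25 mmol/mL an 80 kg patient needs 32 mL even at 0.1 mmol/kg, and at 0.5 mmol/mL a 136 kg patient needs 27.2 mL; both exceed one ampule. A fixed 20 cc can match a per-kilogram dose only approximately. This stands. The argument supports the lower dose by order of magnitude and does not prove it.

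Fourth, neither section gives an injection rate or duration, and a mechanical injector can run at a controlled speed. The words conflict, but the difference cannot be quantified.

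**Conclusion.** The inconsistency is real in the text as supplied: a factor of ten in dose (80 against 8 mmol at 80 kg) and opposing descriptions of the injection. The probable error is the figure in 3.2.1 b). That is an inference from the 20 cc volume and 20 ml ampules in 8.3, and it rests on two assumptions: that 3.2.1 b) means the agent listed in 8.3, and that its concentration lies somewhere near 0.25 to 1.0 mmol/mL. The factor of ten depends on neither concentration nor weight.

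The matter concerns patient safety, not inference. The dose-escalation rule, the MTD and the sample size are unaffected. It applies only to patients who have dynamic contrast MRI; their number is not stated, and total accrual is 18 to 36. The documents do not allow the size of any harm to be estimated. Because this is an operative dosing instruction that is easily corrected, it must be fixed.

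**What to change.** 1. Check the figure in 3.2.1 b) against the source document, and have radiology and pharmacy confirm the intended dose and mode of injection.
2. Amend 3.2.1 b) to 0.1 mmol/kg body weight of the agent named in 8.3, with a cross-reference to that section.
3. State one mode of injection in both sections. Section 8.3 now specifies a bolus by mechanical injector; if slow injection is intended, 8.3 must change as well.
4. Check any other study document that repeats the contrast dose.

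The cost is a one-line amendment to 3.2.1 b), possibly a matching line in 8.3, and the document check. No analysis, sample size or escalation rule changes.

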### 3.2.2 *Tissue Collection*

#### 3.2.2.1 General co-registration guidelines

Co-registration of the biopsy site to an MRI image will be accomplished by one of the following options: 1) real-time MR guidance of the biopsy procedure, 2) placing fiducial markers visible on MRI to identify sites selected for future biopsy, 3) fusing images from CT or Ultrasound-guided biopsy procedures to MR images, 4) repeat MRI immediately after a biopsy procedure to identify needle tracts.

Tissue will be collected with standard biopsy procedures (outlined below). NSAIDS should be discontinued one week prior to a biopsy procedure unless it is deemed unsafe or violates with the treatment protocol. Note that a separate consent specific to each biopsy procedure will be obtained.

### **3.2.2.2 Prostate biopsy**

Needle biopsies will be performed in collaboration with surgeons from the Urologic Oncology Branch-NCI, and Radiologists from the Clinical Center-NIH. During each procedure, 2-10 samples will be obtained using 14-18 gauge tru-cut needles.

Biopsies will be performed according to standard techniques as follows. Patients undergo antibiotic prophylaxis with a quinolone antibiotic for one or two days before biopsy and the morning of biopsy. If the patient is known to be allergic to this antibiotic or if they experience an allergic reaction to it, a different one, such as Bactrim, will be prescribed. A rectal enema is self-administered. Patients void and then are placed in the prone position or in the left- or right-lateral decubitus position. A transrectal ultrasound or MRI probe (custom designed coil, approved by NMR Center Research Safety Subcommittee) is inserted and imaging measurements of the prostate obtained. After initial imaging is obtained, transperineal (or transrectal) introduction of 10-20 cc 1% lidocaine or 10cc of 0.25% bupivacaine is administered along the paraprostatic neurovascular bundle and the tip of the seminal vesicle. After 3 minutes of dwell time, transperineal (or transrectal), targeted prostate biopsy is performed as directed by imaging and 3-D spatialization (i.e. in the x,y,z coordinates). The patient recovers in the supine position and is allowed to ambulate shortly thereafter with a normal mean blood pressure. The patient is required to void without difficulty prior to discharge. Prostate biopsy is extremely well tolerated with complications occurring in 1% due mostly to infection, which can be treated in most cases with parenteral or enteral antibiotics as adjudged by the clinician.

### **3.2.2.3 Tissue Handling**

[name] should be notified prior to specimen collection. Unless otherwise directed by [name], samples will be delivered to [name], [contact].

Samples will be divided at the time of the procedure. Half will be immediately fixed in formalin and submitted to the Laboratory of Pathology, NCI, for histopathological analysis. The remaining tissue will be placed in freezer vials and immediately frozen in liquid nitrogen.

#### 3.2.2.4 Tissue Analysis

A diagnostic pathological evaluation will be performed on the specimens in collaboration with the laboratory of pathology – NCI. Supplementary tests, including but not exclusive to immunohistochemistry and counts of microvessel density, may be performed in a pilot exploratory fashion at the discretion of the principal investigator.

Tissue samples may then be processed for microarray testing. RNA will be isolated and pooled from the cell population of interest. Depending on the number of cells captured, amplification strategies may be explored. Using the total RNA, probes will be prepared and hybridized to a human microarray chip. Microarray analysis will then proceed with the mAdb analysis tools available to NIH investigators (nciarrray.nci.nih.gov). Other software will be used as needed.

Tissue specimens collected in the course of this research project may be banked and used in the future to investigate new scientific questions related to this study. However, this research may only be done if the risks of the new questions were covered in the consent document.

No germline mutation testing will be performed on any of the samples collected unless the patient gives separate informed consent. Tests will be pilot studies related to the Branch's work on such topics as molecular imaging, molecular profiling, and novel molecular therapeutics. If any research tests are considered to be themselves of more than minimal risk to the patients, separate permission will be requested from the IRB to perform that test, and a new consent will be obtained.

At the completion of the protocol, the investigator will dispose of all specimens in accordance with the environmental protection laws, regulations and guidelines of the Federal Government and the State of Maryland.

Any loss or unintentional destruction of the remaining samples will be reported to the IRB.

### *3.2.3 Radiation Therapy*

#### *3.2.3.1 Treatment planning*

PTV1 will be defined as the prostate with a 3 mm uniform margin. The prescription dose to PTV1 will be 7560 cGy in 180 cGy daily fractions. Consistent with the RTOG 9406 data, no volume 4 mm beyond PTV1 will be allowed to receive a dose beyond 100% of the prescription dose. This will be the highest priority constraint for treatment planning. Lesser doses to PTV2 and PTV3 will be accepted in order to maintain this constraint.

PTV2 will be defined as regions of signal abnormality (plus a 2 mm margin) on MRI that do not have a pathologic confirmation of disease. Dose will be escalated by protocol (see section 3.1.2).

PTV3 will be defined as regions of signal abnormality (plus a 2 mm margin) on MRI that do have pathologic confirmation of disease. Dose will be determined by protocol. If the patient previously had at least a sextant biopsy with documentation of the location of the positive cores, this information may be used to define a PTV3. In this case, the physician will determine the volume.

If indicated, the seminal vesicles may also be contoured and treated. When indicated, the seminal vesicles may be treated to 5400 cGy in 180 cGy.

### 3.2.3.2 Summary Of Dose Constraints:

#### Highest Priority:

- PTV1 will be defined as the prostate with a 3 mm uniform margin. The prescription dose to PTV1 will be 7560 cGy in 180 cGy daily fractions. No volume 4 mm beyond PTV1 will be allowed to receive a dose beyond 100% of the prescription dose.
- The prostatic urethra, as defined by the attending physician, will attempt to be limited to 7800 cGy.
- Maximum dose to the rectum and bladder will also attempt to be limited to 7800 cGy.
- Less than 25% of the rectal volume will be irradiated to 7000 cGy.

#### Secondary Priority:

- PTV2 and PTV3 will be taken to full dose as per protocol.
- No more than 40% of the bladder will receive more than 6500 cGy.

### 3.2.3.2 Radiation Treatment

Patients should begin their radiation treatment once pathology is available. In general patients will receive external beam radiation in the NCI Radiation Oncology Clinic daily, Monday – Friday except holidays.

### 3.3 TREATMENT MODIFICATIONS

Modifications to the radiation treatment will be discussed with the Principal Investigator or Study Chairperson. Isocenter adjustments will be performed for prostate motion greater than 5 mm. In each dose cohort, the attending physician may accept a final plan that delivers 107 to 93% of the prescription dose to PTV 1-3. Larger deviations will require prior approval of the PI.

### 3.4 ON-STUDY EVALUATION

#### 3.4.1 *Pre-Procedure (baseline)*

- Informed consent obtained
- Clinical evaluation
  - History and physical exam
  - Vital signs
  - Pathology report confirming adenocarcinoma of the prostate
- Laboratory evaluation
  - PSA
  - PT/PTT
  - CBC
- EPIC (Appendix IIIC)
- AUA Symptom Score (Appendix IV)
- Sexual Heath Inventory for Men (SHIM) (Appendix V)

